13.0 Recruitment Methods

13.1 Subjects will be recruited from the surgery unit pre-op area. They will be identified by reviewing OR schedules in Epic.

14.0 Withdrawal of Subjects*

14.1 Patients experiencing severe pain with VAS scores >7 at the surgical site will be considered as failed FNB or sciatic nerve block and will be withdrawn from the study.

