- 6.3 Group 1: Patients will receive up to 20 mL of 0.5% ropivacaine with epinephrine 1:200,000 and 0.2 mg/ml of dexamethasone for FNB and up to 20 mL of 0.5% ropivacaine with epinephrine 1:200,000 and 0.2 mg/ml of dexamethasone for sciatic nerve block under ultrasound guidance, the total dose not to exceed 3 mg/kg of ropivacaine (total volume 1.5 mL/kg of 0.2% ropivacaine). For patients who weigh less than 30 kg, the volume of the local anesthetic will be reduced to keep the total dose at \leq 3 mg/kg.

Group 2: Patients will receive up to 20 mL of 0.5% ropivacaine with epinephrine 1:200,000 and 0.2 mg/ml of dexamethasone for FNB and up to 20 mL of 0.5% ropivacaine with epinephrine 1:200,000 and 0.2 mg/ml of dexamethasone for posterior knee capsular infiltration under ultrasound guidance (IPACK), the total dose not to exceed 3 mg/kg of ropivacaine. For patients who weigh less than 30 kg, the volume of the local anesthetic will be reduced as needed to keep the total dose at \leq 3 mg/kg.

- 6.4 For intraoperative increases in heart rate or systolic blood pressure $\geq 20\%$ above the baseline, fentanyl (1 µg/kg) will be administered every 5 minutes until the heart rate is below this threshold. Prophylaxis for postoperative nausea and vomiting will include ondansetron (0.1-0.15, maximum 4 mg). At the conclusion of the procedure, all patients will receive ketorolac (0.5 mg/kg, maximum 30 mg).
- 6.5 Patients experiencing severe pain with VAS scores >7 at the surgical site will be considered as failed FNB or sciatic nerve block and will be withdrawn from the study. In the postoperative care unit, the nursing staff will be blinded to which group the patient was assigned to, reducing bias. Fentanyl (1 μ g/kg, maximum 50 μ g) will be administered every 5-10 minutes as needed until the patient's visual analogue score (VAS) score is \leq 4. VAS will be evaluated every hour until discharge. When the patients are ready for discharge and tolerating oral intake, analgesia will be changed to hydrocodone with acetaminophen, 1 tablet by mouth if needed, prior to discharge home.

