- 6.6 Patients will be discharged home with postoperative pain medication to include hydrocodone with acetaminophen. Parents will be instructed to administer one tablet every 4 hours as needed when the VAS score is greater than 4. If the patient does not tolerate hydrocodone, the patient will be given the option for ibuprofen 10 mg/kg every 6 hours. Caregivers will be given a diary to record the amount of pain medication consumed, pain scores (every 4-6 hours), and the duration of motor block as reported by the patient. On postoperative day 1(or 2 for a later discharge), a member of the study team will call to collect the information for a total of 24 hours following hospital discharge. The study investigator will also contact the patients 2 weeks after the procedure to assess for any adverse events not detected during the initial data collection.

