12.0 Local Number of Subjects

- 12.1 50
- 12.2 Sample size will be determined according to previous studies in adults. Abdallah et al. described the non-inferiority of the IPACK block over 24 hours postoperatively, while Kim et al. described superiority of IPACK with respect to pain scores at rest and ambulation, as well as opioid consumption, over postoperative days 0-1. With the greatest pain observed on POD0, our study will be powered for comparing the maximal pain score on POD0 between the 2 groups. Based on the data presented by Abdallah et al., we anticipate that pain scores over POD0 would differ by no more than 1 point between the groups, on a 0-10 scale. Based on the data presented by Kim et al., we hypothesize a standard deviation of pain scores of 1.1. Following Abdallah et al, our study will be powered for a test of IPACK non-inferiority, such that the null hypothesis will

be rejected if pain scores in the IPACK group are >1 point greater than in the control group. Under these assumptions, an unpaired onetailed t-test would attain 90% power for rejecting the null hypothesis at a 95% confidence level when at least 22 patients are enrolled in each group. We propose enrolling a total of 50 patients to account for non-normal distribution of the primary outcome; protocol violations resulting in subject exclusion; and missing data.

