17.0 Data Management* and Confidentiality

17.1 Continuous outcomes will be compared between groups using 2sample t-test or rank-sum tests according to the normality of the distribution (checked by the Shapiro-Wilk test). Categorical outcomes will be compared between groups using Chi-square or Fisher's exact tests, according to cell size.

- 17.2 Research records will be stored in a locked cabinet and password protected computer. Only certified research personnel will be given access to identifiable subject information
- 17.3 Following publication of study results, research records will be stored for a period of 3-5 years and then will be destroyed by placing in a secure shredding bin.

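### Withdrawal at VAS above 7 selects on the outcome the trial is powered on, and nothing keeps these scores in the analysis; excluding them in both arms could inflate false non-inferiority

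*Combined protocol and SAP*

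**What the plan says.** Section 12.2 sets the powered comparison: "our study will be powered for comparing the maximal pain score on POD0 between the 2 groups". The scale is 0-10, the non-inferiority margin 1 point and the SD 1.1. A one-tailed t-test at 95% confidence has 90% power with at least 22 per group. Enrolment is 50, and the surplus is meant to cover non-normality, "protocol violations resulting in subject exclusion; and missing data".

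Sections 6.5 and 14.1 carry the same rule: patients with "VAS scores >7 at the surgical site will be considered as failed FNB or sciatic nerve block and will be withdrawn from the study".

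On pain measurement, Section 6.5 says "VAS will be evaluated every hour until discharge". Under Section 6.6, scores then go into a home diary every 4 to 6 hours and are collected by telephone on postoperative day 1 or 2. An investigator is also to "contact the patients 2 weeks after the procedure to assess for any adverse events".

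The analysis text is in Section 17.1: "Continuous outcomes will be compared between groups using 2sample t-test or rank-sum tests", chosen by a normality check. It gives no analysis set, no missing-data rule and no statement about withdrawn patients.

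**The concern.** The rule removes randomised patients because of a value of the outcome being compared. That value arises after randomisation and may be caused by the assigned block. In a non-inferiority trial, cutting off the top of the scale takes more patients from the worse arm, which moves the estimate towards the conclusion the trial hopes to reach.

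The text leaves four things open:

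- **Analysis.** It does not say whether the triggering score, or any later score, is analysed. Section 12.2 ties exclusion only to protocol violations.
- **Arm.** The wording names failed FNB or sciatic block, not IPACK. Every patient receives FNB, so the rule can be read as covering both arms, but it could also be applied to the sciatic arm alone.
- **Time window.** None is given. A score above 7 at home would be known only when the diary is collected.
- **Follow-up.** It is unclear whether the diary and the 2-week adverse-event contact continue after withdrawal.

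If these points are settled after the data are seen, the main conclusion can depend on how they are settled.

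**Working it through.** **Inputs.** From Section 12.2: margin 1, SD 1.1, one-sided 5%, 22 per group, 50 enrolled (25 per arm). From Sections 6.5 and 14.1: cut-off 7. Assumed, because the documents are silent: control means of 3 to 5.5, an alternative SD of 2, and how the rule is applied. Section 12.2 words the null hypothesis the wrong way round. I took the usual test: non-inferiority is claimed if the one-sided 95% upper limit of IPACK minus control is below 1.

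**Step 1: the plan's own figure.** With truly equal arms, power = 1 − F(t₀.₉₅; df, δ), where F is the noncentral t distribution, df = 2n − 2 and δ = 1/(1.1 × √(2/n)). For n = 22, δ = 1/(1.1 × 0.3015) = 3.015 and power is 90.7%. For n = 21 it is 89.4%. The stated 22 per group is reproduced.

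**Step 2: one case by hand.** Take control mean 5, IPACK mean 6 and SD 1.1, with all scores above 7 excluded in both arms. Let z = (7 − mean)/1.1. The share lost is 1 − Φ(z), and the mean of those remaining is mean − 1.1 × φ(z)/Φ(z).

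- Control: z = 1.818; lost 3.45%; remaining mean 5 − 1.1 × 0.0764/0.9655 = 4.913.
- IPACK: z = 0.909; lost 18.17%; remaining mean 6 − 1.1 × 0.2639/0.8183 = 5.645.
- Apparent difference: 5.645 − 4.913 = 0.73 instead of 1.00.
- Expected loss: 25 × (0.0345 + 0.1817) = 5.4 patients, against 50 − 44 = 6 spare.
- An arm falls below 22 if it loses 4 or more. By the binomial distribution, the chance of losing 3 or fewer is 0.990 (control) and 0.310 (IPACK). At least one arm falls short in 1 − 0.990 × 0.310 = 69% of trials.

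**Step 3: false non-inferiority rate.** Simulation with 40,000 trials per case, normal scores clipped to 0-10, 25 per arm, pooled t-test, IPACK truly 1 point worse.

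| Handling of scores above 7 | Mean 3 | Mean 4 | Mean 5 | Mean 5.5 |
|---|---|---|---|---|
| All kept, SD 1.1 | about 5% | about 5% | about 5% | about 5% |
| All excluded, both arms, SD 1.1 | 5% | 8% | 23% | 40% |
| Same, whole-number scores | 5% | 6% | 13% | 24% |
| Half excluded, both arms, SD 1.1 | 5% | 6% | 10% | 12% |
| Triggering score kept, later scores lost, SD 1.1 | 5% | 5% | 7% | 9% |
| Excluded in sciatic arm only, SD 1.1 | 5% | 5% | 3% | 1% |
| All excluded, both arms, SD 2 | 10% | 14% | 22% | 27% |

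In the fifth row the triggering score is drawn uniformly between 7 and the true maximum. A repeat with 20,000 trials per case, without clipping for continuous scores, gave 23.5% at mean 5, SD 1.1 (13.0% with whole numbers). At SD 2 it gave 8.7%, 14.0% and 23.0% at means 3, 4 and 5.

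**Step 4: truly equal arms.** At mean 5 and SD 1.1, both arms lose 3.45%, or 50 × 0.0345 = 1.7 patients, and the expected difference stays 0.0.

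**The case against.** The harm is conditional. At the planned SD, a large inflation needs the triggering score to be deleted, the rule to apply in both arms, IPACK to be about 1 point worse, and a control mean near 5 or higher. The documents state none of these, and Section 2.3 hypothesises equal efficacy. At mean 4 and SD 1.1 the rate is only 8%, or 6% with whole-number scores. Other readings give little inflation or a conservative test. On this view the plan shows an ambiguity, not a demonstrated bias.

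That stands as a limit on size. It does not remove the problem. A type I error rate is judged at the margin, whatever the investigators expect. The spread from 1% to 40% across readings and assumed means is itself the reason to fix the reading in advance.

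Two narrower points also have weight. The trigger concerns pain at the surgical site, while Section 12.2 names no site, so excluding every score above 7 is an upper bound; the half-excluded row brackets this. Section 12.2 also allows for missing data, where withdrawn patients might be counted. That protects numbers, but it does not correct selection on the outcome.

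Finally, stating how the scores are handled would remove the ambiguity without adding block failure as an outcome. That is true, but an explicit rule to exclude them in both arms would keep the bias. The scores have to be kept.

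**Conclusion.** The concern holds and must be fixed. Followed on its natural reading, the rule selects on the powered outcome, and no text prevents this. With IPACK truly 1 point worse and SD 1.1, exclusion in both arms takes the false non-inferiority rate from 5% to between 5% and 40% over control means 3 to 5.5, and between 5% and 24% with whole-number scores.

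Confidence in the size is medium, because the control mean and the meaning of withdrawal are assumptions. At SD 1.1 and a mean of 3 or less the effect is negligible. With equal arms there is no bias in the difference, and applying the rule to the sciatic arm alone reverses the bias. That the documents leave the choice open is certain. The clinical threshold of 7 is not judged here.

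**What to change.** - **Sections 6.5 and 14.1:** record VAS above 7 as block failure in either arm, IPACK included, without withdrawal from data collection or analysis. State the time window in which it is recorded. Keep the observed score in the maximal POD0 outcome, and continue the diary and the 2-week contact for these patients.
- **Section 17.1:** state that all randomised patients are analysed as assigned. Report block failure by arm as a secondary outcome. Exclude failures only in a sensitivity analysis.

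Clinical care does not change.

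**Cost.** Wording in three sections. The assessments are already scheduled and need only continue for the few patients who would otherwise leave: about 5 of 50 in the mean 5, SD 1.1 case with IPACK 1 point worse, and about 2 of 50 if the arms are equal.

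The real downside is that keeping high scores may push the SD above 1.1. By the formula in Step 1, with 25 per arm and equal means, power is 94% at SD 1.1, 85% at 1.3 and 75% at 1.5. The sponsor should check the sample size against that range.

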1.0 Study Summary

Study Title	Comparison of postoperative analgesic efficacy of femoral	
	nerve block with IPACK versus femoral and popliteal sciatic	
	nerve block in patients undergoing arthroscopic anterior	
	cruciate ligament reconstruction.	
Study Design	Prospective study	
Primary Objective	The primary objective of the study is to compare the	
	analgesic efficacy of FNB with IPACK versus FNB with	
	sciatic nerve block in patients undergoing ACL repair by	
	monitoring postoperative pain scores.	
Secondary	The secondary objective is to show a decreased incidence of	
Objective(s)	adverse effects including motor blockade with IPACK	
	compared to sciatic nerve block and to demonstrate that it is	
	technically less challenging by showing a decreased time	
	required for performance of the block.	
Research	Patients will receive up to 20 mL of 0.5 % ropivacaine with	
Intervention(s)/	epinephrine 1:200,000 and 0.2 mg/ml of dexamethasone for	
Investigational	FNB-AC and up to 20 mL of 0.5% ropivacaine with	
Agent(s)	epinephrine 1:200,000 and 0.2 mg/ml of dexamethasone for	
	sciatic nerve block or posterior knee capsular infiltration.	
IND/IDE #	N/A	
Study Population	Patients undergoing elective anterior cruciate ligament	
	reconstruction.	
Sample Size	50	
Study Duration for	Total of 2 weeks.	
individual		
participants		
Study Specific	IPACK – infiltration of the posterior knee capsule	
Abbreviations/	FNB - Femoral nerve block	
Definitions	PACU – post-anesthesia care unit	
	POD – post-op day	

2.0 **Objectives**

- 2.1 The primary objective of the study is to compare the analgesic efficacy of FNB with IPACK versus FNB with sciatic nerve block in patients undergoing ACL repair by monitoring postoperative pain scores.
- 2.2 The secondary objective is to show a decreased incidence of adverse effects including motor blockade with IPACK compared to sciatic nerve block and to demonstrate that it is technically less challenging by showing a decreased time required for performance of the block.
- 2.3 We hypothesize that FNB with IPACK provides the same analgesic efficacy as FNB with sciatic block while avoiding the motor blockade associated with sciatic nerve block.

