5.0 Study Intervention/Investigational Agent

5.1 Study subjects will receive up to 20 mL of 0.5% ropivacaine with epinephrine 1:200,000 and 0.2 mg/ml of dexamethasone for FNB and up to 20 mL of 0.5% ropivacaine with epinephrine 1:200,000 and 0.2 mg/ml of dexamethasone for sciatic nerve block under ultrasound guidance or posterior knee capsular infiltration under ultrasound guidance (IPACK), the total dose not to exceed 3 mg/kg of ropivacaine.

5.2 Both the FNB and sciatic nerve blocks are considered standard of care at NCH. The IPACK is not currently performed at NCH.

6.0 **Procedures Involved***

- Following informed consent, patients will be randomized into one of 6.1 the two groups. Intraoperative anesthetic care will not vary from our usual practice. Patients requiring preoperative anxiolysis will receive oral midazolam (0.3-0.5 mg/kg, maximum 20 mg) 30 minutes prior surgery or intravenous midazolam (0.05 mg/kg, maximum 2 mg) prior to transport to the operating room. Standard American Society of Anesthesiologists' monitors will be placed. Once in the operating room, anesthesia will be induced by the intravenous or inhalational route as clinically indicated. All subjects will receive propofol (2-3 mg/kg) and fentanyl (2µg/kg). Following the induction of anesthesia, an appropriately sized laryngeal mask airway (LMA) will be placed. After the regional anesthesia time out, patients will receive the block based on the group assigned from a randomization list created by www.sealedenvelope.com. The time from the initiation of the timeout for the block until the patient has been returned to the surgical position will be noted.
- 6.2 The following demographic and surgical parameters will also be collected and recorded: patient age, gender, race/ethnicity, height, weight, ASA status, primary diagnosis, list of comorbidities, procedure date and duration, admission status, intraoperative medications and postoperative medications, PACU arrival and discharge times, discharge destination, pain scores (including recorded time), regional anesthetic time and dose, postoperative opioids consumed and time of hospital admission and discharge.

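### Treated patients with VAS >7 are withdrawn from the study, and nothing keeps them in the follow-up calls or in the adverse-effect comparison of objective 2.2

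*Combined protocol and SAP*

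**What the plan says.** Section 14.1 is a single rule: a patient with VAS above 7 at the surgical site "will be considered as failed FNB or sciatic nerve block and will be withdrawn from the study". Section 6.5 repeats it. Neither place limits the withdrawal to the efficacy analysis, makes an exception for safety follow-up, or gives a time window.

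The block is given after induction of anesthesia: in 6.1, "patients will receive the block based on the group assigned from a randomization list". No postoperative VAS exists until later.

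Section 6.6 sets two contacts after discharge. On POD 1 (or 2), "a member of the study team will call to collect the information for a total of 24 hours following hospital discharge"; this covers medication, pain scores and patient-reported duration of motor block (endpoint 4.6). The investigator will also "contact the patients 2 weeks after the procedure to assess for any adverse events not detected during the initial data collection". Withdrawn patients are not mentioned for either contact.

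Objective 2.2 depends on these data: "The secondary objective is to show a decreased incidence of adverse effects including motor blockade with IPACK compared to sciatic nerve block". For the analysis, 17.1 says only "Categorical outcomes will be compared between groups using Chi-square or Fisher's exact tests, according to cell size". No intention-to-treat, safety or as-treated population is defined anywhere.

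**The concern.** A patient can be withdrawn under this rule only after being exposed to the study injections, and the trigger is itself an outcome of the block. If withdrawal ends participation, two things follow.

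- **Follow-up.** The 2-week contact is the only listed procedure that names adverse events, and the data list in 6.2 has no adverse-event item. A patient withdrawn before discharge would miss that contact and the diary call. No other safeguard is described: 18.1 leaves monitoring to the study investigators alone.
- **Comparison.** Objective 2.2 is a between-arm claim about incidence. Dropping patients because their block failed means the groups compared are no longer the groups randomised. The losses need not be equal. IPACK is not currently performed at the site (5.2), and the rule names a failed FNB or sciatic block but not a failed IPACK, so its application in Group 2 is unclear.

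This point concerns safety follow-up and the adverse-effect denominator. What the same rule does to the maximal POD0 pain score is a separate matter.

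**Working it through.** The plan gives no figure for this point. Its only related figure, 22 per group (12.2), reproduces: margin 1, SD 1.1, one-sided 5% and 90% power give 21 by normal approximation, and the t-test has 89.4% power at 21 and 90.7% at 22. Nothing below changes it.

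**Step 1. What a withdrawn patient would still contribute, reading the text plainly**

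| Source | When | If withdrawn in PACU or phase 2 | If VAS >7 is learned at the POD 1/2 call |
|---|---|---|---|
| Motor and sensory block (4.4) | PACU, phase 2 | May have been recorded; retention not stated | Recorded; retention not stated |
| Motor block duration (4.6, via 6.6) | POD 1/2 call | Missed | Collected at that call; retention not stated |
| Adverse events (6.6) | 2 weeks | Missed | Missed |

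The word missed is an inference from withdrawal from the study. Section 22.2 uses the same expression for a family that chooses to leave, which supports reading it as the end of participation.

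**Step 2. How many patients**

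The documents give no VAS >7 rate. Assume 5-20% of the 50 enrolled:

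- 5%: 0.05 × 50 = 2.5
- 10%: 0.10 × 50 = 5
- 20%: 0.20 × 50 = 10

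**Step 3. Direction and size of the error in one arm**

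Let w be the share withdrawn, p_R the adverse-effect rate in retained patients and p_W the rate in withdrawn patients. All treated patients have rate (1 − w)p_R + w·p_W, while an analysis of retained patients reports p_R. The error is

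p_R − [(1 − w)p_R + w·p_W] = w(p_R − p_W).

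Its sign depends on whether p_R or p_W is larger, which the documents do not tell us. Its absolute value cannot exceed w. Two illustrations, with every rate assumed:

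- *Overstatement.* Motor blockade in 80% of successful and 20% of failed sciatic blocks, with 15% failing: 0.85 × 80% + 0.15 × 20% = 71% in all treated patients, against 80% reported. The error is +9 points in the sciatic arm, which would favour IPACK. It arises only if PACU assessments of withdrawn patients are left out.
- *Understatement.* Adverse effects in 10% of successful and 30% of failed blocks, with failure of 10% in one arm and 20% in the other: 0.9 × 10% + 0.1 × 30% = 12%, and 0.8 × 10% + 0.2 × 30% = 14%. Both arms would report 10%.

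**Step 4. Loss of information even without bias**

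If an arm shows no events, the one-sided 95% upper bound on its event rate is 1 − 0.05^(1/n). Assuming 25 per arm and equal withdrawal:

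- n = 25 (none withdrawn): 11.3%
- n = 22 (about 10% withdrawn): 12.7%
- n = 20 (20% withdrawn): 13.9%

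**The case against.** The strongest reply is that no sentence says the calls stop or that collected data are discarded. Section 6.6 assigns the contacts to the patients without excluding anyone, and 17.1 removes nobody from the adverse-effect comparison. Staff might make the calls anyway. This is fair: loss of contact is the natural reading, but still an inference. The withdrawal itself is stated outright, in two places, and nothing qualifies it.

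Second, motor blockade is the only adverse effect that 2.2 names, and 4.4 assesses it in PACU and phase 2 recovery. Section 6.6 presents the 2-week contact as a supplement to earlier detection. A VAS above 7 learned at the POD 1/2 call would not cost that call. All of this stands. It rules out a reading that a reader might infer, that withdrawn patients yield no adverse-effect data at all.

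Third, a reader might infer that failed blocks carry more adverse effects, so that the rule hides events. The documents do not support that direction, and a failed sciatic block could plausibly produce less motor blockade. In the understatement example the true gap is also small: at 25 per arm, 12% and 14% are 3.0 and 3.5 expected events.

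Finally, the documents do not say that the study calls are the only clinical contact after surgery, so they do not show that late complications would go unnoticed in care. What they show is that the trial would have no stated means of recording them for these patients.

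**Conclusion.** The concern holds in a limited form. The protocol withdraws already-treated patients on a post-randomisation outcome of the block and keeps them in neither the 6.6 contacts nor the 2.2 comparison. What is most clearly at risk is motor block duration for patients withdrawn before discharge, and the 2-week adverse-event contact for any patient withdrawn before it takes place. PACU and phase 2 assessments may survive, but the text does not say so.

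The resulting bias can run either way, and its size cannot be derived. At an assumed withdrawal rate of 5-20%, about 2 to 10 of 50 treated patients are affected, and the error in an arm's incidence is at most 5 to 20 percentage points, a ceiling reached only if retained and withdrawn patients have opposite extremes of incidence. The documents do not support a claim that events in a particular arm would be concealed. The text should be corrected because the gap touches both safety follow-up and the fairness of a stated objective, and closing it is cheap.

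**What to change.** 1. In 14.1, 6.5 and 6.6, state that a patient who meets the VAS >7 criterion after receiving a block remains in follow-up, with the POD 1/2 call and the 2-week contact made as for every other patient, unless consent is withdrawn.
2. In the same places, state that data collected before the criterion was met, including the PACU and phase 2 block assessments, are kept.
3. In 17.1, state that adverse effects, including motor blockade, are reported by randomised arm for all patients who received a block, with the number meeting the VAS >7 criterion shown for each arm.
4. State how the criterion applies in Group 2, since the wording names FNB and sciatic block only.

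These changes concern follow-up, retention and reporting, and leave the clinical handling of severe pain as it is. The cost is a few sentences and, at the assumed rates, the calls for about 2 to 10 patients that are already planned for everyone else.
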